7.7 Withdrawal Criteria

Subjects **may** withdraw from the trial for any of the following reasons:

1. Unacceptable treatment efficacy: the (sub)investigator is free to withdraw the subject at any time based on a medical judgment.
2. Unacceptable AEs or LSRs: any AEs or LRS that the (sub)investigator or the subject considers unacceptable.
3. Exclusion criteria: any exclusion criteria which emerge/become apparent during the subject's participation in the clinical trial.
4. Voluntary withdrawal: subjects are free to withdraw from the clinical trial at any time and for any reason.
5. Subjects must withdraw from the trial for any of the following reasons:
 - a. Subject becomes pregnant during the trial.
 - b. Subject with positive pregnancy test at screening and/or Day 1 will be excluded and complete End of Trial Form. Subjects with positive pregnancy test at visits after treatment (Week 2, 4, 8, or 12) may remain in trial for follow up.

Reason(s) for withdrawal must be recorded in the eCRF and medical records.

Subjects who are discovered, after enrolment/randomisation, not to have fulfilled all in-/exclusion criteria at the time of enrolment should discontinue treatment unless the (sub)investigator, based on clinical and ethical evaluation, finds discontinuation inappropriate.

Subjects who discontinue treatment after at least one treatment should remain in the trial for follow-up assessments. AEs should be followed up in all subjects as described in section 9.5

Subjects withdrawn will not be substituted.

8 Trial Schedule and Assessments

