11.1 Determination of Sample Size

With a sample size of 38 subjects the power of observing a difference between active and vehicle gel will be 84% in a trial with intraindividual comparisons, using a paired two-sided t-test on a 5% level, assuming an approximate total lesion count of 36 at baseline and reductions at end of trial from baseline around 7.3 (20%) and 12.4 (34%) for vehicle gel and active respectively, and a standard deviation of the difference between treatments at end of treatment up to 10.4.

The assumptions on sample size are that all but the two first subjects of the 40 subjects randomised are included in the efficacy analyses, and the assumptions on efficacy rely on experiences from a previous trial conducted by LEO in subjects suffering from acne vulgaris

(LP0045-01), together with an expected reduction in standard deviation of the primary endpoint of at least 20% due to the intraindividual comparisons.

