11.3.4 Analysis of Primary Endpoints

11.3.4.1 Total lesion count

The evaluation of the treatment effect on total lesion count (inflammatory and non-inflammatory) lesions at Week 12 (primary endpoint) will be performed within the framework of an ANCOVA model with treatment as fixed effect, baseline total lesion count as covariate and subject as random effect.

Comparison between active and vehicle gel will be done by means of a t-test on the estimated treatment contrast in the model. Estimated difference, 95% confidence limit and test probability will together with least square means and their 95% confidence limits be presented from the model.

A sensitivity analysis investigating potential effect of lateral side of lesion will be performed by adding this effect to the above model.

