11.3.12 Handling of Missing Values

Subjects with missing counts of inflammatory and non-inflammatory lesions at visits 7, 8 and 9 (weeks 2, 4 and 8) will be excluded from the analyses based on FAS and PP for these time points, and missing lesion counts will therefore not be imputed for these subjects. For subjects with missing lesion counts at visit 10 (week 12), the missing lesion counts of visit 10 will be imputed and the endpoints will be derived afterwards from the imputed values.

A multiple imputation method will be used to handle missing data. The imputation method relies on the assumption that the missing data are missing at random (MAR), i.e. the probability that an observation is missing can depend on observed data but is unrelated to the data not observed. All imputations will be performed by lesion type and treatment group.

Imputation of missing values for subjects with a monotone missing data pattern (i.e. there exist a time point for the subject where all observations before the time point are present and all later observations are missing) will be based on the full observed dataset excluding subjects with a non-monotone missing data pattern. The missing values for lesion counts at visit 10 will be imputed sequentially from a linear regression model with lesion counts at previous visits as covariates and treatment compliance (as identified by means of protocol deviations) as factor.

For subjects with a non-monotone missing data pattern, the lesion counts at visit 10 will be imputed using data from subjects without a non-monotone missing data pattern based on the Markov Chain Monte Carlo (MCMC) method including compliance effect, and lesion counts at previous visits 7, 8 and 9 as continuous variables. In case of non-convergence the compliance effect will be excluded from the imputation model. The imputed values at visit 10 will be rounded to the nearest non-negative integer.

Table 5 shows seed and numbers of imputations used for the multiple imputations

Sensitivity analyses of the method of handling missing data will be performed for the analyses of the imputed endpoints: last observation carried forward (LOCF) and an observed cases approach.

Table 5 Parameters defining imputation of lesion counts

Assessment	Seeds for Imputation for subjects with monotone pattern of missing data	Seeds for Imputation for subjects with non-monotone pattern of missing data	Number of imputations
Inflammatory lesions	255951	897661	100

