Appendix 10: Identifying and Documenting the Treatment Area

Appendix 11: Acne QoL

Appendix 12: TSQM II

25 Appendix 1: Protocol Summary

Name of finished/ investigational product	LEO 43204 gel 0.018%
Name of active substance	LEO 43204
Title of trial/trial ID/	Explorative trial evaluating the efficacy, tolerability and safety of LEO 43204 applied in a split-face (left/right) topical design in adults with moderate to severe acne / EXP-1223
International Coordinating Investigator	[name].
Sponsor's name/ address	LEO Pharma A/S, [name]
Estimated number of trial sites and distribution	Single site in USA
Trial period	Planned date of enrolment of first subject: Q2-2016 Planned date of completion of last subject: Q4-2016
Main objective(s)	To assess the efficacy of treatment with LEO 43204 gel and vehicle gel on acne vulgaris disease severity 12 weeks after end of treatment. Treatment is defined as once daily application of LEO 43204 gel and vehicle gel for up to 3 days
Methodology	Phase 2a, Single centre, prospective, randomised, vehicle-controlled, double-blinded, split-face (left/right) design trial
Number of subjects to be enrolled	Planned to enroll 40 subjects Planned to complete 30 subjects
Main criteria for inclusion	
 • Subjects should be diagnosed with moderate to severe acne vulgaris of the face. • Fitzpatrick skin types I-III (due to lack of safety data for the investigational product in darker skin types) • Lesions should be relatively symmetrical in appearance on both sides of the face (asymmetrical disposition of acne lesions defined as: the number of acne lesions on any hemiface is greater than twice the number on the other hemiface for either inflammatory or non-inflammatory lesions). • Male or female aged 18 to 35 years inclusive.

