4.3.1 Analysis of primary endpoint

The analysis of the primary endpoint total lesion count at week 12 will follow the description in the protocol. The primary analysis will be based on the FAS analysis set. A sensitivity analysis will include the lateral side of lesion as

a covariate. An additional sensitivity analysis will be performed on the PP analysis set.

Furthermore, if there are missing data then the above analyses will be handled with the below multiple imputation methods and additionally an LOCF and an OC analysis will be included.

Missing data for total lesion count on day 1 or week 12 will be handled using multiple imputation as described in the protocol. The following additional specifications may be given:

- All imputations will be performed by lesion type and treatment group.
- Total lesion will be calculated by summing of inflamed and non-inflamed lesions by simulation

Screening and baseline lesion values are very similar. To avoid problems with identifiability in the estimations modeling will only be from baseline and forward.

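### Missing Week 12 counts are imputed cheek by cheek and lesion type by lesion type, so the standard error of the paired primary contrast can be mis-sized in either direction

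*Protocol*

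**What the plan says.** Protocol 11.3.12 sets the strata for multiple imputation: "All imputations will be performed by lesion type and treatment group". SAP 4.3.1 repeats the rule and adds: "Total lesion will be calculated by summing of inflamed and non-inflamed lesions by simulation". For monotone patterns the Week 12 count comes from a "linear regression model with lesion counts at previous visits as covariates and treatment compliance" as a factor. Non-monotone patterns use MCMC with the counts at Weeks 2, 4 and 8 and compliance. Neither document brings the other cheek's count, or a shared subject term, into the draw. SAP 4.3.1 also imputes missing Day 1 counts.

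The rest of the plan is paired. Protocol 11.3.4.1 fits an ANCOVA with "baseline total lesion count as covariate and subject as random effect". Protocol 11.1 uses a paired t-test and an "expected reduction in standard deviation of the primary endpoint of at least 20% due to the intraindividual comparisons". SAP 4.3.2 replaces Fisher's test with McNemar's for IGA success because the observations are paired.

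On the likely amount of missing data, Appendix 1 of the protocol has "Planned to complete 30 subjects" out of 40 enrolled, while Protocol 7.7 has "Subjects who discontinue treatment after at least one treatment should remain in the trial for follow-up assessments". Observed-case and LOCF sensitivity analyses are planned.

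**The concern.** A missed Week 12 visit loses both cheeks. The plan then draws the two cheeks' residuals independently, and within each cheek the two lesion types independently. The first split removes a correlation that should shrink the variance of the active-minus-vehicle difference. The second removes one that should enlarge the variance of each side's total. Rubin's rules carry both errors into the primary standard error.

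At stake is the precision of the one formally tested efficacy contrast in a 38-subject trial whose size was justified by within-subject comparison. The imputed primary analysis could be less powerful than its own observed-case sensitivity analysis, or could report an interval slightly too narrow.

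**Working it through.** **1. The plan's own figure.** Protocol 11.1 gives n = 38, a difference of 12.4 − 7.3 = 5.1, SD of the difference 10.4, and a two-sided 5% test. The noncentrality is 5.1/(10.4/√38) = 3.02 on 37 df, so power is 83.7%. The stated 84% reproduces.

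**2. Implied correlation between cheeks.** A 20% reduction ending at 10.4 starts from 10.4/0.8 = 13.0.
- If 13.0 is the per-side SD, 1 − correlation = 10.4²/(2 × 13²) = 0.32, so the correlation is 0.68.
- If 13.0 is the SD of an unpaired difference, the per-side SD is 13/√2 = 9.19 and 1 − correlation = 0.8² = 0.64, so the correlation is 0.36.

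The protocol does not say which.

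**3. What own-side history leaves.** What matters is r, the correlation of the cheeks' Week 12 residuals given each cheek's own four earlier visits (Day 1, Weeks 2, 4, 8). Take unit variance and a cheek correlation of 0.68; the variance shares are assumptions.
- *Stable subject effect only.* Weight per visit 0.68/(1 + 3 × 0.68) = 0.2237. Residual variance 1 − 4 × 0.2237 × 0.68 = 0.392. Residual covariance 0.68 − 2 × 0.895 × 0.68 + 0.2237² × 16 × 0.68 = 0.008. So r ≈ 0.02: own-side history already carries the pairing.
- *Middle setting.* Shares 0.50 stable subject, 0.18 shared by the cheeks at one visit only, 0.07 stable side-specific. Weight 0.57/(1 + 3 × 0.57) = 0.2103. Residual variance 0.520. Residual covariance 0.68 − 2 × 0.841 × 0.50 + 0.2103² × (4 × 0.68 + 12 × 0.50) = 0.225. So r = 0.43. If the shared visit variation has autocorrelation (AR) 0.5, 0.7 or 0.85, r is 0.36, 0.29 or 0.20.

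**4. Direction of the error.** Let each lesion type on each cheek have residual variance v, with correlation ρ between types and r between cheeks, and assume that these multiply. The true residual variance of the difference in totals is 4v(1 + ρ)(1 − r). Four independent draws give 4v. The ratio, plan to truth, is 1/[(1 + ρ)(1 − r)]:
- r = 0.36: 1.56 at ρ = 0, 1.04 at ρ = 0.5, 0.87 at ρ = 0.8
- r = 0.20, ρ = 0.8: 0.69
- r = 0.02, ρ = 0.3: 0.78

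The two errors cancel at ρ = r/(1 − r): 0.75 for r = 0.43, 0.56 for r = 0.36, 0.25 for r = 0.20.

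**5. Simulated standard error** (2,000 runs, 100 imputations, 8 of 38 pairs missing, visit correlation 0.6, no rounding). Mean Rubin SE over true SD under the plan:

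| r | ρ = 0 | ρ = 0.5 | ρ = 0.8 |
|---|---|---|---|
| 0.20 | not used here | not used here | 0.97 |
| 0.36 | 1.13 | 1.04 | 1.00 |
| 0.68 | 1.36 | not used here | not used here |

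Imputing the cheeks together gave 1.04 at ρ = 0 for both r = 0.36 and r = 0.68, so about 4 points of excess there is not due to the split. Planned interval width relative to imputing the cheeks together (ρ = 0, r from 0.36 to 0.68) was 1.03–1.10 at 2 missing, 1.06–1.20 at 4, and 1.10–1.35 at 8. At r = 0 the effect vanished.

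**6. Simulated power loss against observed cases**, with the plan's rounding to non-negative integers, shares as in the middle setting:
- 8 missing, ρ = 0.3: 5.7, 7.8 and 11 points in three simulations that differ in detail. In the third, power was 62% against 73%, and mean SE 2.07 against a true 1.77.
- 8 missing, AR 0.7: 5.5 (ρ = 0.3), 2.0 (ρ = 0.6), none (ρ = 0.8). AR 0.85, ρ = 0.6: 0.3.
- 4 missing: 2.4 (AR 0, ρ = 0.3), 1.2 (AR 0.7, ρ = 0.3), none (AR 0.7, ρ = 0.6).

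Without the floor at zero, 2 missing cost under 1 point, and a stable subject effect with 8 missing cost nothing (a gain of 1–2 points). At ρ = 0.8 the plan's SE fell slightly below the true SD (1.81 against 1.86; 2.46 against 2.54).

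**7. Type I error under completely random dropout:** 1.7–3.8% with visit-specific shared variation; 5.7% (Monte Carlo SE 0.4) with a stable subject effect.

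The compliance factor and the non-monotone MCMC step were not modelled.

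**The case against.** The strongest case against is that no document supplies the inputs. The correlations, variance shares and dropout timing are all assumed. Eight missing pairs rests on one line of Appendix 1 and on all 30 completers being among the 38. Protocol 11.1 counts on all 38, treatment lasts at most three days, and Protocol 7.7 keeps subjects who stop treatment in follow-up. The observed-case analysis preserves complete pairs and is prespecified. The trial is exploratory phase 2a. The random-subject model is still fitted after imputation, so the passages do not literally contradict each other. All of this stands, and it limits the weight of the point. It does not remove the mechanism: if pairs are missing, the primary result carries the mis-sized interval and the better-behaved analysis is only a sensitivity analysis.

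Two stronger readings are tempting. A reader might infer that the interval is too wide whenever pairs are missing and the cheeks stay correlated. The documents do not support that, because the same sentence also splits by lesion type and step 4 shows that this can cancel or reverse the effect.

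A reader might also infer bias, since the plan's missing-at-random definition says "the probability that an observation is missing can depend on observed data", which includes the other cheek. If dropout is assumed to follow the observed active-minus-vehicle difference (odds multiplied by e per SD), the planned estimate shifts by 0.05 to 0.57 lesions, against 0.05 or less with pair-preserving imputation and up to 0.35 with observed cases. Type I error is then 1.9–6.8%. No document describes such a mechanism, and the shift is small beside the assumed effect of 5.1.

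**Conclusion.** The point holds as a mis-sized standard error whose direction the documents do not determine. It is too large when the cheeks stay positively correlated after own-side history and the lesion types are weakly correlated. It is about right or slightly too small when the types are strongly positively correlated, or when the cheek correlation is a stable subject effect. Under completely random dropout the main cost is precision, with no material bias.

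At an assumed 8 of 38 missing pairs, the power loss against observed cases runs from roughly 6–11 points (shared visit-specific variation, lesion-type correlation 0.3) to about nil. At 4 missing it is a few points or fewer, at 2 it is small, and with none missing it is nil. No single figure in that range can be defended from the documents. The change is cheap and worth making, between optional and should-fix, with medium confidence.

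**What to change.** Before unblinding, through the SAP update that Protocol 11.3.11 allows, specify for the primary total count only:

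- Impute with one record per subject, so that both cheeks are imputed together and the total is imputed directly. For example, regress the active-minus-vehicle difference and, separately, the sum on the same quantity at earlier visits and on compliance; recover the two side counts; round to non-negative integers.
- Use the same structure for non-monotone patterns and for missing Day 1 counts.
- Keep the by-type imputations for the lesion-type endpoints only.

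Both splits need correcting. Joining the cheeks but keeping the types separate gave an SE of 0.94 of the true SD at r = 0.36, ρ = 0.8.

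Costs: new SAP wording, a restructured imputation dataset and a seed for the total in Table 5; no new data. The imputed total no longer equals the sum of the imputed types, so the SAP 4.3.1 summing rule must be limited to the lesion-type endpoints.

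The sum/difference form assumes similar variances and symmetric coefficients on the two sides. With the active-side SD at 0.82 of vehicle (the ratio of Protocol 11.1's Week 12 means, (36 − 12.4)/(36 − 7.3) = 23.6/28.7), simulated bias was 0.01 and type I error 4.8%. An unrestricted joint model using both full histories avoids the assumption but stayed 2–7 points below observed-case power at this sample size.

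The change corrects the standard error; it does not promise more power than observed cases. In the third simulation of step 6 it reached 69%, against 62% for the plan and 73% for observed cases.

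### Both imputation models leave out subjects who skipped an interim visit, so some observed Week 12 counts do not inform the imputation of missing ones; the loss is small and the fix almost free.

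*Protocol*

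**What the plan says.** Protocol section 11.3.12 imputes lesion counts only at Week 12, separately by lesion type and treatment, assuming data missing at random. It describes two steps.

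- For monotone gaps, a sequential linear regression on earlier counts and compliance, which "will be based on the full observed dataset excluding subjects with a non-monotone missing data pattern".
- For non-monotone gaps, the Week 12 count "will be imputed using data from subjects without a non-monotone missing data pattern based on the Markov Chain Monte Carlo (MCMC) method", with compliance and the Week 2, 4 and 8 counts in the model.

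The section calls a pattern monotone when everything is observed up to some time point and nothing after it. No reason is given for restricting the fitting data.

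SAP section 4.3.1 keeps the method: missing Day 1 or Week 12 totals "will be handled using multiple imputation as described in the protocol". It adds that modelling starts from baseline and that totals are summed within each simulation. Neither addition changes which subjects are used for fitting.

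The full analysis set is 38 (Protocol section 11.2). The Protocol Summary (Appendix 1) expects fewer to finish than the 40 enrolled: "Planned to complete 30 subjects".

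**The concern.** A subject seen on Day 1 and at Weeks 2, 8 and 12, but not at Week 4, shows directly how earlier counts relate to the Week 12 count. That relation is what the imputation model must estimate, yet the plan keeps this subject out of both models. MCMC is designed for arbitrary missing patterns, so that step has no need of the exclusion. Under the stated missing-at-random assumption, all observed counts are usable.

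The restriction matters more in a small trial. Each model has at most 38 cheeks and up to six parameters: an intercept, four earlier visits and compliance. At stake is the width of the confidence interval for the primary comparison when Week 12 counts are missing. Bias and test validity are not in question.

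**Working it through.** **1. The plan's own figure.** Protocol section 11.1 states: "With a sample size of 38 subjects the power of observing a difference between active and vehicle gel will be 84" per cent. The test is a paired t-test at two-sided 5%. The effect rests on assumed "reductions at end of trial from baseline around 7.3 (20%) and 12.4 (34%) for vehicle gel and active respectively". For the paired difference, the section takes an SD of no more than 10.4.

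- Difference: 12.4 − 7.3 = 5.1 lesions.
- Standard error: 10.4/√38 = 1.687.
- Noncentrality: 5.1/1.687 = 3.02, with 37 degrees of freedom.
- Power at two-sided 5%: 83.7%, which reproduces the stated 84%.

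This calculation involves no imputation, so the fitting rule does not change it.

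**2. Who is left out.** The section's definition of a monotone pattern gives:

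| Pattern | Used to fit either model? | Own Week 12 value in ANCOVA |
|---|---|---|
| All visits attended | Yes | Observed |
| Drop-out, nothing seen afterwards | Yes, for what was observed | Imputed (regression) |
| Interim visit skipped, Week 12 attended | No | Observed |
| Interim visit skipped, later visit attended, Week 12 missing | No | Imputed (MCMC) |

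The third row is the point at issue.

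**3. How many subjects.** The documents give no skip rate. If each of the three interim visits is skipped independently with probability q, the chance of at least one skip is 1 − (1 − q)³.

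| q (assumed) | Chance of a skip | Of 30 with a Week 12 count | Of 38 |
|---|---|---|---|
| 3% | 8.7% | 2.6 | 3.3 |
| 5% | 14.3% | 4.3 | 5.4 |
| 10% | 27.1% | 8.1 | 10.3 |

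Simulated averages were about 3, 5 and 9 excluded. With 30 observed Week 12 counts and 8 excluded, 22 remain. With six parameters, residual degrees of freedom fall from 24 to 16.

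**4. Effect on the pooled standard error.** The simulation had 38 subjects, Day 1 plus four follow-up visits, and normal data imputed separately by treatment. It used 20 imputations and Rubin's rules, with all 38 kept in the Week 12 analysis. Assumptions: correlation 0.7 between adjacent visits, left–right correlation 0.5, SD of the difference 10.4, skips at random; 120 trials per row.

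| Missing Week 12 | Skippers | SE, plan's rule | SE, all subjects | Increase |
|---|---|---|---|---|
| 2 | 3 | 1.763 | 1.761 | 0.1% |
| 4 | 4 | 1.883 | 1.880 | 0.2% |
| 8 | 4 | 2.158 | 2.124 | 1.6% |
| 8 | 8 | 2.204 | 2.136 | 3.2% |

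Repeats of the first row with 250 trials gave 0.06% (Monte Carlo error 0.20%) and, at correlation 0.5, 0.16% (0.23%). Two further simulations of 240 trials per setting agree. With about 8 missing counts, the increase was 0.9–1.4% at 3% skips (one simulation only), about 1% and 1.7–2.1% at 5% skips, and about 3% and 3.2–3.7% at 10% skips. With 3 missing counts it was about 0.2%.

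**5. Effect on the actual precision of the estimate.** A separate simulation used conditional-mean imputation. It compared the SD of the treatment estimate under the plan's rule with that from fitting on all subjects (Monte Carlo error of the ratio 0.001–0.004).

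| Missing Week 12 | 3% skips | 5% skips | 10% skips |
|---|---|---|---|
| 2 | 1.000 | 1.000 | 1.006 |
| 4 | 0.999 | 1.002 | 1.001 |
| 8 | 1.001 | 1.002 | 1.015 |

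In the multiple-imputation runs of step 4, the empirical SD did not differ in a consistent direction.

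**The case against.** The best defence is that little is lost. An effect needs missing Week 12 counts and skipped interim visits together. The visit windows in Protocol section 8.1, ±3 days to ±1 week from Week 2 on, make skips less likely. With 2–4 missing Week 12 counts the effect is negligible. The planned observed-cases sensitivity analysis uses every skipper's Week 12 count without any imputation model. All of this stands, and it keeps the point minor.

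The first exclusion also has a technical reason, because sequential regression needs monotone data. That stands for the regression taken alone. Filling the interim gaps by MCMC first meets the need and keeps the subjects, and the plan already uses both methods.

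It may be said that the MCMC sentence concerns only subjects whose Week 12 count is missing, so skippers with an observed count were perhaps not meant. The wording leaves some room, but the section's own definition makes them non-monotone, and the regression sentence excludes them in any case.

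Finally, section 11.3.12 says missing interim counts are not imputed for analysis at those visits. Filling them as intermediates does not breach this. Regressing sequentially through the visits appears to do the same for early drop-outs.

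Three stronger readings are tempting and not supported:

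- **The skipper leaves the primary analysis.** Section 11.3.12 limits the interim exclusion to the visit missed. Removing subjects would give a power of 80.5% at n = 35 or 73.8% at n = 30, but the plan does not remove them.
- **Two to three subjects' worth of information is lost.** Squaring the largest SE ratios (1.032–1.037) gives about 1.07, and 7% of 38 is 2.7. That describes the reported SE in the heaviest assumed setting. The SD of the estimate gives 1.015² ≈ 1.03, roughly one subject, in that setting alone.
- **The exclusion is wholly without reason, or the change wholly without cost.** The regression step has the reason given above, and the fix adds a modelling step.

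**Conclusion.** The point holds as a small inefficiency. Both imputation models omit subjects with a skipped interim visit, so their observed Week 12 counts do not help to impute other subjects' missing ones. Their own counts stay in the primary ANCOVA.

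The pooled SE is about 0–0.2% larger with 2–4 missing Week 12 counts, about 1–2% with 8 missing and about 5 skippers, and about 3–4% with 8 missing and about 9 skippers. It is unchanged if either kind of gap is absent. The actual SD of the estimate rises by about 1.5% at most in the settings tried.

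These sizes rest on assumed skip rates, correlations and normal data. The figure of 8 missing is 38 − 30, taken from the Protocol Summary; it would be 10 if both subjects outside the full analysis set were among the 30 completers, a case not simulated. The tabulated SE simulation used one total count rather than two lesion types, no compliance factor, and 20 imputations where the plan has 100. This is an optional improvement, worth making because it uses data already collected and suits the missing-at-random assumption better.

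**What to change.** In a SAP update before unblinding, which Protocol section 11.3.11 allows, replace the two exclusion clauses of section 11.3.12 with imputation fitted on all FAS subjects:

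1. Within lesion type and treatment, run MCMC on Day 1 and Weeks 2, 4, 8 and 12 to complete each data set to a monotone pattern.
2. Apply the sequential regression to each completed data set to impute the remaining missing Week 12 counts.
3. State that filled interim counts are intermediates only and are not analysed at Weeks 2, 4 and 8.

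The 100 imputations, the LOCF analysis and the observed-cases analysis can stay as they are. The cost is SAP wording and a few program lines, with no new data. The small downside is an added joint-normal step for the interim gaps. The SAP already makes a comparable correction in section 4.3.2, replacing Fisher's exact test with McNemar's test.
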